| Document No.: CSD00074 | Page 3 of 23 |

| | | |
|---------|--|----|
| 8. | STATISTICAL CONSIDERATIONS..... | 15 |
| 8.1. | STUDY DESIGN AND OBJECTIVES..... | 15 |
| 8.2. | PRIMARY ENDPOINT | 15 |
| 8.3. | SECONDARY ENDPOINT | 15 |
| 8.4. | SAFETY ENDPOINTS | 15 |
| 8.5. | SAMPLE SIZE..... | 15 |
| 8.6. | STATISTICAL ANALYSES..... | 16 |
| 9. | ADVERSE EVENTS..... | 16 |
| 10. | STUDY ADMINISTRATION..... | 16 |
| 10.1. | REGULATORY AND ETHICAL CONSIDERATIONS | 16 |
| 10.1.1. | Informed Consent | 16 |
| 10.1.2. | Institutional Review Board | 16 |
| 10.1.3. | End of the study | 17 |
| 10.2. | INVESTIGATOR RESPONSIBILITIES | 17 |
| 10.3. | DATA MANAGEMENT | 17 |
| 10.4. | STUDY MONITORING | 17 |
| 10.5. | SUBJECT CONFIDENTIALITY | 17 |
| 10.6. | QUALITY ASSURANCE..... | 18 |
| 10.7. | RETENTION OF ESSENTIAL STUDY DOCUMENTS | 18 |
| 10.8. | AGREEMENTS..... | 18 |
| 11. | PUBLICATION | 18 |
| 12. | REFERENCES..... | 18 |

| | |
|--|--|
| Exalenz Bioscience Ltd. | Last update on: April 01, 2015 |
| Protocol: The predictive value of the BreathID, ¹³ C-Methacetin breath test for Hepatic Decompensation; a retrospective analysis | Version Level: 1b |
| Document No.: CSD00074 | Page 4 of 23 |

SYNOPSIS

Investigational Product:

0.05% ¹³C-Methacetin solution and the BreathID® Device

Phase of Development:

Retrospective clinical investigation

Background:

This study is a follow up study to be conducted in selected sites, that participated in Exalenz' Pivotal HIS-EX-408 and/or PLT-BID-1108 study using the MBT in chronic liver patients. The aim of the study was to compare the breath test to the liver biopsy to assess the capability to detect cirrhosis.

Study Rationale:

Previous studies have shown that the MBT can be used to predict liver decompensation. In the present study Exalenz wishes to evaluate the prognostic value of MBT and Biopsy in a long term retrospective surveillance of the described study population.

Objectives:

To evaluate the ability of the MBT to predict hepatic decompensation events, in patients with chronic liver disease.

Primary outcome measures: MBT results and Hepatic decompensation measured with the time to each event, defined as the occurrence of at least one of the following events in the time frame between the last ¹³C-Methacetin Breath Test (MBT) to the time of data collection:

1. Death (liver related)
2. Transplantation (cadaveric and living donors)
3. Ascites
4. HE (Hepatic Encephalopathy)
5. Newly diagnosed varices or variceal bleeding
6. SBP (spontaneous bacterial peritonitis)/Sepsis
7. HRS (Hepatorenal syndrome)
8. HCC (hepatocellular carcinoma)
9. Increase in CTP (Child Turcotte Pugh) Score by 3 points
10. Increase in MELD score by 5 points

Primary Endpoints:

Time to the first occurrence of a hepatic decompensation event (as defined in the primary outcome measures).

Secondary endpoints:

| | |
|--|--|
| Exalenz Bioscience Ltd. | Last update on: April 01, 2015 |
| Protocol: The predictive value of the BreathID, ¹³ C-Methacetin breath test for Hepatic Decompensation; a retrospective analysis | Version Level: 1b |
| Document No.: CSD00074 | Page 5 of 23 |

- Histological liver biopsy results (obtained in the initial study) versus clinical outcome at time of current data collection
- Time to each of the individual events as follows:
 1. Death (liver related)
 2. Transplantation (cadaveric and living donors)
 3. Ascites
 4. HE (Hepatic Encephalopathy)
 5. Newly diagnosed varices or variceal bleeding
 6. SBP (spontaneous bacterial peritonitis)/Sepsis
 7. HRS (Hepatorenal syndrome)
 8. HCC (hepatocellular carcinoma)
 9. Increase in CTP (Child Turcotte Pugh) Score by 3 points.
 10. Increase in MELD score by 5 points

Study Design: Retrospective, multicenter clinical evaluation of patients' outcome initially enrolled (n=414+165=579) into the Exalenz pivotal studies (protocols HIS-EX-408 and/or PLT-BID-1108 respectively). The information collected in this study will be anonymous.

Study Population: A maximum of 579 adult male or female patients enrolled into the Exalenz studies (protocols HIS-EX-408 and/or PLT-BID-1108) who performed a ¹³C-Methacetin Breath Test.

Main Inclusion Criteria: Patient has been tested with the MBT in the past Exalenz pivotal studies protocols HIS-EX-408 and/or PLT-BID-1108 (from August 2008 to September 2012).

Main Exclusion Criteria: Patient had been enrolled into the pivotal study but not included in the final analysis due to conditions / factors interfering with the MBT (i.e. exclusion criteria within the HIS-EX-408 and/or PLT-BID-1108 study).

Statistical Analysis:

Introduction:

It is anticipated that 3-5% of patients with stable cirrhosis will develop hepatic decompensation and achieve an end-point within a year. An additional 1-2% would be expected to die from these complications per year. This study is conducted 6 years post initial enrollment, accordingly the expected amount of complications are expected to be 6 times higher. Furthermore some of the patients that were not considered as cirrhotic at the time of enrollment may progress to cirrhosis and deteriorate.

| | |
|--|--|
| Exalenz Bioscience Ltd. | Last update on: April 01, 2015 |
| Protocol: The predictive value of the BreathID, ¹³ C-Methacetin breath test for Hepatic Decompensation; a retrospective analysis | Version Level: 1b |
| Document No.: CSD00074 | Page 6 of 23 |

All patients with valid breath test results from the HIS-EX-408 and/or PLT-BID-1108 trials will be candidates for this follow up trial.

Analyses:

All statistical analyses and data presentations, including tabulations and listings, will be performed using the SAS version 9.3 (or higher) software. Statistical tests will be two-sided and the level of significance is 0.05. Nominal p-values will be presented.

The ability of MBT to predict morbidity and mortality and other complications will be evaluated using survival analysis methods, mainly Kaplan-Meier curves and Cox regression analyses.

| | |
|--|--|
| Exalenz Bioscience Ltd. | Last update on: April 01, 2015 |
| Protocol: The predictive value of the BreathID, ¹³ C-Methacetin breath test for Hepatic Decompensation; a retrospective analysis | Version Level: 1b |
| Document No.: CSD00074 | Page 7 of 23 |

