In general, declining liver function and an increase in the CTP and/or MELD scores appear prior to complications of cirrhosis; gastrointestinal bleeding from portal hypertension (variceal and non-variceal), ascites, spontaneous bacterial peritonitis (SBP), hepatic encephalopathy (HE), hepato-renal syndrome (types 1 and 2) and HCC. Patients are considered to have stable cirrhosis when they have normal or near-normal hepatic function and no prior complications of cirrhosis. Such patients have a CTP score of less than 7; reflective of Childs class A cirrhosis. Approximately 3-5% of patients with stable Child class A cirrhosis will develop worsening in hepatic function and/or complications of cirrhosis and decompensate on a yearly basis. In many patients the development of these complications, the deterioration in global liver function and the rise in MELD is a slow gradual process which allows sufficient time for successful transplantation. In contrast, approximately one-third of patients with cirrhosis develop rapid hepatic decompensation a precipitous rise in MELD and die from complications of cirrhosis before they can either be considered for or receive a liver transplant. This observation explains why pre-transplant mortality for patients on the UNOS waiting list is actually greatest in patients with low MELD, not high MELD scores. It is currently believed that such patients have marginal hepatic metabolic capacity or hepatic reserve which both places them at risk for developing complications of cirrhosis and for rapid deterioration when complications occur.

1.2. Identifying patients with marginal hepatic reserve at risk for complications and decompensation:

Tests to assess hepatic metabolic function are conducted by administering either intravenously or orally a compound with high hepatic extraction ratio and/or rapid hepatic metabolism. The rate at which the parent compound is removed from the serum or a metabolic product of the parent compound appears in either the blood, urine, breath or saliva reflects hepatic metabolic function. Some of the compounds which have been successfully

| | |
|--|--|
| Exalenz Bioscience Ltd. | Last update on: April 01, 2015 |
| Protocol: The predictive value of the BreathID, ¹³ C-Methacetin breath test for Hepatic Decompensation; a retrospective analysis | Version Level: 1b |
| Document No.: CSD00074 | Page 8 of 23 |

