3. ENDPOINTS

3.1. Primary Efficacy Endpoints

The MBT results and the time to hepatic decompensation events:

Hepatic decompensation is defined as the occurrence of at least one of the following events in the time frame between the last ¹³C-Methacetin Breath Test (MBT) to the time of data collection:

1. Death (liver related)
2. Transplantation (cadaveric and living donors)
3. Ascites
4. HE (Hepatic Encephalopathy)
5. Newly diagnosed varices or variceal bleeding
6. SBP (spontaneous bacterial peritonitis)/Sepsis
7. HRS (Hepatorenal syndrome)
8. HCC (hepatocellular carcinoma)
9. Increase in CTP (Child Turcotte Pugh) Score by 3 points
10. Increase in MELD score by 5 points

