10.1.2. Institutional Review Board

Before initiation of the study at a given center, written approval of the protocol, and waiver for the Informed Consent Form must be approved from the appropriate IRB. If any amendments to any of these documents occur during the study, written approval must be obtained prior to their implementation.

| | |
|--|--|
| Exalenz Bioscience Ltd. | Last update on: April 01, 2015 |
| Protocol: The predictive value of the BreathID, ¹³ C-Methacetin breath test for Hepatic Decompensation; a retrospective analysis | Version Level: 1b |
| Document No.: CSD00074 | Page 17 of 23 |

10.1.3. *End of the study*

For administrative reporting purposes the end of the study will be defined as the date of the final clinical database lock. This provides for a single and conservative definition across all study sites.

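### Does the Synopsis's six-fold event projection need correcting, given that patients will not all have six years of follow-up?

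*Combined protocol and SAP*

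**What the plan says.** The Statistical Analysis part of the Synopsis opens with an annual rate: "It is anticipated that 3-5% of patients with stable cirrhosis will develop hepatic decompensation" and reach an endpoint within a year, with another 1-2% dying of these complications each year. It continues: "This study is conducted 6 years post initial enrollment, accordingly the expected amount of complications are expected to be 6 times higher". It then adds, without a figure, that some patients who were not cirrhotic at enrollment may progress. Section 1.1 gives the same yearly rate: "Approximately 3-5% of patients with stable Child class A cirrhosis".

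The dates are elsewhere. The Main Inclusion Criteria in the Synopsis place the source studies "from August 2008 to September 2012". The page header reads "Last update on: April 01, 2015". Section 3.1 opens each patient's event window at the last test and closes it at data collection: "Breath Test (MBT) to the time of data collection". Section 10.1.3 says, for administrative reporting, that "the end of the study will be defined as the date of the final clinical database lock". Neither closing point has a calendar date. Section 10.1.2 implies that collection starts after the document date, since approval comes first: "Before initiation of the study at a given center, written approval of the protocol".

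Section 8.5 gives a maximum of 414 + 165 = 579 subjects, with no event target and no power. Section 8.6 specifies Kaplan-Meier curves, the log-rank test and Cox regression.

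**The concern.** The sentence uses one follow-up time as a multiplier, although entry was spread over about four years. Only patients tested by about April 2009 had six years behind them when the document was dated. Reading initial enrollment as the first patient's enrollment explains where the six years come from. It does not justify scaling expected complications by the longest follow-up in the cohort.

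In a survival analysis, precision depends on events rather than on patients. Section 8.5 says nothing about events, so this sentence is the plan's only guide to how many might accrue over the whole follow-up. If it is too optimistic, a reader could expect more information from the stable-cirrhosis patients than the data will hold. The missing cut-off date means the factor cannot be verified.

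**Working it through.** **Inputs.** Annual decompensation rate 3-5% and factor 6 (Synopsis, Statistical Analysis); August 2008 to September 2012 (Synopsis, Main Inclusion Criteria); document date 1 April 2015 (page header); clock from last test to data collection (section 3.1). The even spread of tests and the later cut-off dates below are assumptions; the documents give neither.

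**The plan's own figure.** Years × annual rate: 6 × 3% = 18% and 6 × 5% = 30%. The factor of 6 follows if mean follow-up is 6 years and risk adds linearly.

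**Follow-up at the document date.**
- Earliest test, 1 August 2008 to 1 April 2015: 6.66 years.
- Latest test, 30 September 2012 to 1 April 2015: 2.50 years.
- Width of the window: 6.66 − 2.50 = 4.16 years, or 50 months.
- Mean if tests are evenly spread: (6.66 + 2.50) / 2 = 4.58 years.
- Linear projection at that mean: 4.58 × 3% = 13.7% and 4.58 × 5% = 22.9%.

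**Dependence on the cut-off.** Under even spread, a later cut-off adds the same time to every patient. The excess is 6 / mean − 1, and the share with six years is (maximum − 6) / 4.16.

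| Cut-off | Mean follow-up (years) | Excess of 6 over the mean | Share with 6 years |
|---|---|---|---|
| 1 April 2015 | 4.58 | 31% | 16% |
| End 2015 | 4.58 + 0.75 = 5.33 | 13% | 34% |
| 1 April 2016 | 4.58 + 1.00 = 5.58 | 7.5% | 40% |

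The mean reaches 6 when 6 − 4.58 = 1.42 years have been added, around the end of August 2016. After that the factor of 6 is too low. Every patient reaches six years only from about the end of September 2018.

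**Dependence on accrual.** Without assuming even spread, an April 2015 cut-off supports a factor of 6 only if the mean last-test date is about 1 April 2009, which is 8 months into the 50-month window. For April 2016 it would be about 1 April 2010, 20 months in. Two studies of unequal size (414 and 165) are pooled without separate dates, so the true mean is unknown.

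**First events.** At a constant annual risk r, the proportion with a first event by six years is 1 − (1 − r)^6. For r = 3% this is 1 − 0.97^6 = 16.7%, a factor of 5.57. For r = 5% it is 1 − 0.95^6 = 26.5%, a factor of 5.30. The sentence speaks of the amount of complications rather than first events, so this is a different quantity and not a correction of the stated one.

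**Where the factor is used.** Nowhere else. Section 8 does not repeat it. Section 8.5 takes its number from the source studies, and no analysis in section 8.6 has it as an input.

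**The case for a change.** The best case for a change is that the conflict lies within the document, the arithmetic is not in dispute, and replacing one sentence is cheap. Survival analyses depend on events, and this is the only place where the plan says how many to expect over the whole follow-up. A rewrite could also put a date on the close of the event window.

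The factual part stands: six years is not a common follow-up time, and the plan does not derive the factor. The rest is weaker.

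- The rates are given for stable cirrhosis and the next sentence treats other patients separately, so the factor should not be read as covering all 579.
- The quoted period may be the duration of the source studies rather than the dates of the first and last tests. In that case the range of 2.5 to 6.7 years gives outer limits.
- The size of the error, and even its direction, depends on two unknowns: the cut-off and the accrual pattern.
- A better factor would not give an event count. The number of patients with stable cirrhosis is not stated, and events in other patients are not quantified.
- A per-patient projection would need test dates, baseline Child class and record length. Record length becomes known only through the chart review, which is the study itself.
- A date placed in a background sentence would not alter the endpoint definition or section 8.6. Each patient's window already has a rule for its end, data collection, and an analyst would apply it patient by patient.

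**Conclusion.** No change follows. The six-fold statement is a rough background expectation that ignores staggered entry. At the document date it overstates mean follow-up by about 31%, if the quoted period is the test window, tests were evenly spread and records are complete. Under the same assumptions the overstatement is 13% at the end of 2015 and 7.5% at April 2016, and it is gone by about the end of August 2016.

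Nothing in the study depends on the figure. The sample is the patients available from two completed studies, no power claim or event target is made, and Kaplan-Meier and Cox methods accommodate unequal follow-up. When results are reported, the actual follow-up and observed events replace the projection. Correcting the sentence would tidy the text without altering the data collected, the analyses or the conclusions they can support.

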1. BACKGROUND INFORMATION

1.1. Clinical outcome in patients with chronic liver disease

Chronic liver disease is the 9th most common cause of death in the United States. Unfortunately, mortality secondary to chronic liver disease, cirrhosis and its complications is expected to increase in the future. This is primarily due to the maturation of the Hepatitis C Virus (HCV) epidemic, a rising rate of hepatocellular carcinoma (HCC) and an increasing prevalence of non-alcoholic steatohepatitis (NASH).

Mortality in patients with chronic liver disease is typically confined to patients with cirrhosis; and the mortality risk in these patients has long been assessed by the Child-Pugh-Turcotte (CTP) score. More recently, the Model of End-Stage Liver Disease (MELD) has been shown to more accurately predict 30 day survival in patients with cirrhosis. The MELD score is now utilized by the United Network for Organ Sharing (UNOS) to prioritize patients awaiting liver transplantation. Those factors which contribute to the CTP scoring systems are: Bilirubin, INR, albumin, ascites, encephalopathy and creatinine. The MELD score uses only blood tests and is thus less prone to subjective assessments such as ascites or encephalopathy.

In general, declining liver function and an increase in the CTP and/or MELD scores appear prior to complications of cirrhosis; gastrointestinal bleeding from portal hypertension (variceal and non-variceal), ascites, spontaneous bacterial peritonitis (SBP), hepatic encephalopathy (HE), hepato-renal syndrome (types 1 and 2) and HCC. Patients are considered to have stable cirrhosis when they have normal or near-normal hepatic function and no prior complications of cirrhosis. Such patients have a CTP score of less than 7; reflective of Childs class A cirrhosis. Approximately 3-5% of patients with stable Child class A cirrhosis will develop worsening in hepatic function and/or complications of cirrhosis and decompensate on a yearly basis. In many patients the development of these complications, the deterioration in global liver function and the rise in MELD is a slow gradual process which allows sufficient time for successful transplantation. In contrast, approximately one-third of patients with cirrhosis develop rapid hepatic decompensation a precipitous rise in MELD and die from complications of cirrhosis before they can either be considered for or receive a liver transplant. This observation explains why pre-transplant mortality for patients on the UNOS waiting list is actually greatest in patients with low MELD, not high MELD scores. It is currently believed that such patients have marginal hepatic metabolic capacity or hepatic reserve which both places them at risk for developing complications of cirrhosis and for rapid deterioration when complications occur.

1.2. Identifying patients with marginal hepatic reserve at risk for complications and decompensation:

Tests to assess hepatic metabolic function are conducted by administering either intravenously or orally a compound with high hepatic extraction ratio and/or rapid hepatic metabolism. The rate at which the parent compound is removed from the serum or a metabolic product of the parent compound appears in either the blood, urine, breath or saliva reflects hepatic metabolic function. Some of the compounds which have been successfully

| | |
|--|--|
| Exalenz Bioscience Ltd. | Last update on: April 01, 2015 |
| Protocol: The predictive value of the BreathID, ¹³ C-Methacetin breath test for Hepatic Decompensation; a retrospective analysis | Version Level: 1b |
| Document No.: CSD00074 | Page 8 of 23 |

utilized for this purpose include choline, caffeine, galactose, aminopyrine, erythromycin, lidocaine and methionine and Methacetin [N-(4-Methoxy-phenyl) acetamide]. Previous studies utilizing a battery of liver function tests have demonstrated that these tests correlate with worsening fibrosis and cirrhosis. The hepatic metabolism of lidocaine to monoethylglycinexylidide (MEGX) has been shown to decline with increasing liver fibrosis and with worsening stages of cirrhosis, improve with successful treatment of the underlying liver disease, and to accurately predict which patients with stable cirrhosis awaiting liver transplantation were at risk to develop future hepatic decompensation. Unfortunately, administering lidocaine to perform this test is associated with parasthesias and could precipitate cardiac arrhythmias. Thus, while promising as a potential liver function test the use of lidocaine for this purpose has been largely abandoned.

1.3. Identifying patients with progression of liver disease and fibrosis at earlier stages (pre-cirrhosis) of liver disease:

Chronic liver patients that have varied levels of fibrosis based on biopsy need to be monitored for progression of disease as well. A significant percentage of these patients in earlier stages of liver disease have recurrent normal blood tests in the standard liver panel blood tests. Additionally, even patients where the blood tests do show irregular values, the values do not always correlate with disease progression and a non-invasive test that is both safe and accurate would be very beneficial to monitor their liver health. This is especially important in decision making regarding the decision to begin treatment when signs of disease progression are apparent to prevent deterioration to cirrhosis. Furthermore, a non-invasive test is necessary to monitor these patients once they begin treatment in order to assess the effectiveness of the treatment.

1.4. Breath Tests

Breath tests that are based on monitoring the ¹³CO₂, which is a by-product of ¹³C labeled substrates metabolism by the liver, have been proposed as a tool for non-invasive evaluation of liver health and have been used for over 30 years.

Methacetin may be utilized for the evaluation of liver functional capacity and/or the extent of liver impairment. The biochemical basis for the evaluation of functional capacity is that the compound is metabolized by the cytochrome P450 enzyme CYP1A2. Diseases of the liver that cause a loss in functional mass and/or impact the metabolic function of CYP1A2 in hepatic microsomes hepatocytes are associated with and may be correlated to a decrease in the liver capacity to metabolize Methacetin.

One of the most common methods for determining the rate of metabolism of Methacetin is to analyze the rate of metabolism of the methoxy group (CH₃O) of Methacetin to carbon dioxide, which is excreted in exhaled breath. To distinguish the carbon dioxide derived from Methacetin from all other sources of carbon dioxide, the methoxy group is labeled with ¹³C, a stable isotope of carbon. Thus all the CO₂ derived from Methacetin will contain ¹³C (¹³CO₂) in contrast to all other sources of CO₂, which will contain approximately 99% ¹²C, and 1% ¹³C, the naturally abundant isotope. Thus, the rate of excretion of CO₂ (normalized

| | |
|--|--|
| Exalenz Bioscience Ltd. | Last update on: April 01, 2015 |
| Protocol: The predictive value of the BreathID, ¹³ C-Methacetin breath test for Hepatic Decompensation; a retrospective analysis | Version Level: 1b |
| Document No.: CSD00074 | Page 9 of 23 |

to CO₂) above background following the administration of Methacetin-methoxy-¹³C indicates its rate of metabolism, which relates to the hepatic cell "health" and to the functional mass of the liver.

1.5. BreathID® System:

Exalenz has developed the BreathID device to perform automatic breath tests based on a unique molecular correlation spectrometer (MCS). Based on specific optical-radiation emission and absorption by ¹³CO₂ and ¹²CO₂ gases, the portable BreathID MCS device continuously senses exhaled breath and analyzes CO₂ in real-time through a nasal cannula worn by the patient. The primary output of the BreathID is the PDR (percentage dose recovery) and CPDR (Cumulative PDR) which quantify the amount of ¹³C labeled substrate metabolized by the liver..

1.6. ¹³C-labeled substrate - ¹³C-Methacetin:

The substrate used in the pivotal study breath test was ¹³C- Methacetin whose resultant ¹³CO₂ can be measured in the exhaled breath. The amount of metabolized Methacetin indicates the capability of the liver to accomplish one of its main physiological tasks and has been shown to correlate with liver fibrosis and cirrhosis. ¹³C-Methacetin meets all of the qualifications for an in-vivo diagnostic test. It is a non-toxic small molecule. No reports of any complications using this substance have been reported. The compound is considered to remain stable over an extended period of time.

